§ None of the pre-specified doses in the CTP would be allowed based on EWOC, lower doses than the pre-specified ones could be chosen in practice if agreed between sponsor and SMC.

Operating characteristics

Operating characteristics are a way to assess the long-run behaviour of a model by illustrating the precision of the design in estimating the MTD. Under an assumed true dose-toxicity curve, metrics such as the probability of recommending a dose with true DLT rate in the target interval can be approximated via simulation. [Table 10.5: 2](#) describes 7 assumed true dose-toxicity scenarios for Arms A and B which were used to assess the operating

characteristics of the joint model for these arms. The toxicity scenarios reflect a wide range of possible cases as follows:

- Scenario 1: moderate-toxicity scenario
- Scenario 2: high-toxicity scenario
- Scenario 3: low-toxicity scenario
- Scenario 4: non-logistic dose-toxicity scenario
- Scenario 5: all planned doses in overdose range

For Arms A and B, two additional scenarios were used to assess the operating characteristics, especially to assess the effect of the interaction between BI 1387446 and ezabenlimab (BI 754091).

- Scenario 6: data for ezabenlimab (BI 754091) largely deviates from data for BI 1387446, represented by a very flat dose-toxicity curve (as indicated by currently available data on ezabenlimab (BI 754091)) that lies in the overdose range (indicating a quite toxic behaviour of BI 1387446, contrarily to the ezabenlimab (BI 754091) data, which indicate a very low toxicity overall)
- Scenario 7: Large interaction effect between BI 1387446 and ezabenlimab (BI 754091)

Table 10.5: 2

Assumed true dose-toxicity scenarios for Arms A and B

Scenario	Arm		Dose					
			0.075	0.099	0.136	0.203	0.350	0.524
1: Moderate	A		0.075	0.099	0.136	0.203	0.350	0.524
	B		0.157	0.176	0.210	0.276	0.424	0.566
2: High Tox	A	P(DLT)	0.134	0.179	0.287	0.326	0.478	0.579
	B		0.157	0.206	0.291	0.383	0.490	0.592
3: Low Tox	A		0.014	0.076	0.112	0.185	0.201	0.249
	B		0.081	0.104	0.162	0.198	0.235	0.287
4: Non-Logistic	A		0.014	0.076	0.112	0.326	0.478	0.579
	B		0.081	0.104	0.162	0.383	0.490	0.592
5: All too toxic	A		0.341	0.378	0.403	0.457	0.526	0.599
	B		0.367	0.400	0.489	0.534	0.596	0.626
6: Large deviation	A		0.075	0.099	0.136	0.203	0.350	0.524
	B		0.351	0.356	0.359	0.361	0.368	0.370
7: High interaction	A		0.075	0.099	0.136	0.203	0.350	0.524
	B		0.172	0.211	0.292	0.472	0.780	0.927

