Scenario 3 (low-toxicity scenario) shows that in Arm A around 63% of trials declared MTDs with true DLT rate in the target interval. The majority of the rest of the trials (256 trials) [REDACTED] as the MTD, which has a true DLT rate in the underdose interval. In Arm B around 90% of trials declared a dose as MTD that has an assumed true toxicity rate in the target interval.

Scenario 4 represents a case where the assumed true dose-toxicity curve does not follow a logistic shape. In this scenario, 40.3% of trials in Arm A determined a dose as MTD which

has a true DLT rate in the target interval. Additionally, 475 trials in Arm A declared [REDACTED] as the MTD, which has an assumed true toxicity probability of 0.112. In Arm B, 67.9% of trials declared a dose as MTD which has a true DLT rate in the target interval. In addition to that, 207 trials declared the combination of [REDACTED] 240 mg as MTD which has an assumed true toxicity probability of 0.383, which is close to the upper boundary of the target interval.

In scenario 5, all specified dose levels have an assumed toxicity rate in the overdose interval. In this case most of the simulated trials stop prematurely because all specified dose levels are too toxic. In all 3 arms several simulated trials (Arm A: 13.8%, Arm B: 12.4%) declare doses as MTD with true DLT rate in the overdose interval. Most of these trials choose [REDACTED] or [REDACTED] as MTD. These doses have assumed true toxicity rates not too far away from the target rate therefore this is still acceptable for such overly toxic scenarios.

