In scenario 6, the data for ezabenlimab (BI 754091) largely deviates from the data for BI 1387446. While a flat dose-toxicity curve that lies in the overdose range is assumed for BI 1387446, very low toxicity is assumed for ezabenlimab (BI 754091). This results in high-toxicity for the combination arm B: Many of the simulated trials in Arm B stop prematurely because all specified dose levels are too toxic. Additionally, around 56% of trials in Arm B declare doses as MTD with true DLT rate in the overdose interval. Most of these trials choose [REDACTED] or [REDACTED] as MTD. These combinations have assumed true toxicity rates not too far away from the target rate. In Arm A, 51.6% of the simulated trials declare a dose as MTD which has an assumed true DLT rate in the underdose interval. In almost all of these cases [REDACTED] were chosen as MTD and these dose levels have an assumed true toxicity probability of 0.099 [REDACTED] and 0.136 [REDACTED]

In scenario 7 (high interaction between BI 1387446 and ezabenlimab (BI 754091)), 44.9% of the trials in Arm A declared a dose as MTD which has a true DLT rate in the underdose interval. 314 of these trials declared [REDACTED] as the MTD which has a true toxicity probability of 0.136 which is close to the lower boundary of the target interval. In Arm B around 74% of trials determined an MTD that has an assumed true toxicity rate in the target interval.

The mean patient numbers in Arm A range from approximately 5.6 patients (Scenario 5) to 17.3 patients (Scenario 3) and the maximum number of patients was 36 (Scenario 3). Similarly, for Arm B, the mean patient numbers range from 5.0 (Scenario 5) to 15.6 (Scenario 3), with a maximum number of 45 patients in a simulated trial under Scenario 3. Therefore, the patient numbers are as expected and increase when moving away from the high-toxicity scenario.

By reviewing the metrics presented in [Table 10.5: 3](#), it can be seen that the joint model is not sensitive to different scenarios of truth. Even under misspecification results are satisfactory. In general, these models are conservative due to the overdose control criteria. In all scenarios, the probabilities of recommending a dose with true $P(DLT) \geq 33\%$ as MTD are much smaller than probabilities of recommending a dose with true $P(DLT)$ between 16% and 33% as MTD.

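### Protocol 10.5 claims that an overdose MTD is far less likely than a target MTD in every scenario; its own results contradict this in at least 3 of 14 scenario-arms

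*Protocol*

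**What the plan says.** Section 7 of the protocol defines target toxicity as [0.16, 0.33) and overtoxicity as [0.33, 1.00]. It sends the reader to Section 10.5 for the evaluation of the model. That appendix simulates 1000 trials for each of seven assumed dose-toxicity truths in Arms A and B (Table 10.5: 2).

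The closing assessment contains the sentence that opens "In all scenarios, the probabilities of recommending a dose with true". It states that recommending an MTD with true P(DLT) of 33% or more is far less likely than recommending one between 16% and 33%. It has no qualifier.

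The preceding paragraphs report:

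- Scenario 5, defined as "Scenario 5: all planned doses in overdose range": "In this case most of the simulated trials stop prematurely because all specified dose levels are too toxic", and "several simulated trials (Arm A: 13.8%, Arm B: 12.4%) declare doses as MTD with true DLT rate in the overdose interval".
- Scenario 6, Arm B: "around 56% of trials in Arm B declare doses as MTD with true DLT rate in the overdose interval". The sponsor comments: "These combinations have assumed true toxicity rates not too far away from the target rate".
- Scenario 6, Arm A: "51.6% of the simulated trials declare a dose as MTD which has an assumed true DLT rate in the underdose interval".
- Scenario 7, Arm A: "44.9% of the trials in Arm A declared a dose as MTD which has a true DLT rate in the underdose interval".

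**The concern.** The sentence is the appendix's final statement on how well the design avoids declaring a too-toxic dose as MTD. The MTD is a primary endpoint, and SAP Section 7.4.1 uses the same joint BLRM for its main analysis. The claim covers every scenario, but it fails where all planned doses are too toxic and the desirable outcome is to declare no MTD. A reader who takes only the conclusion would not learn that more than half of the Scenario 6 Arm B trials declare an overdose MTD. A neighbouring sentence calls the results satisfactory even under misspecification and does not mention that figure either.

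**Working it through.** **Inputs.** The true DLT rates are the 14 rows of Table 10.5: 2, with six doses each. The selection percentages come from the scenario paragraphs of Section 10.5. The body of Table 10.5: 3 is not readable in the public document. The simulation was therefore not re-run, and where no overdose percentage is printed only an upper bound is possible.

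**Step 1: classify the doses.** Each true rate is counted as under (<0.16), target [0.16, 0.33) or over (>=0.33).

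**Step 2: compare the percentages.** Where the overdose share is not printed, its upper bound is 100% minus the stated shares that are not overdose (target, underdose, early stop). Printed figures given as approximate make the bounds approximate.

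| Scenario-arm | Doses under/target/over | Target MTD | Overdose MTD | Sentence |
|---|---|---|---|---|
| 1A | 3/1/2 | about 29% | at most 100 - 29 - 28.8 = 42.2% | not checkable |
| 1B | 1/3/2 | about 82% | at most 18% | consistent |
| 2A | 1/3/2 | about 55% | at most 100 - 55 - 41 = 4% | consistent |
| 2B | 1/2/3 | about 61% | at most 100 - 61 - 27 = 12% | consistent |
| 3A | 3/3/0 | about 63% | 0% | consistent |
| 3B | 2/4/0 | about 90% | 0% | consistent |
| 4A | 3/1/2 | 40.3% | at most 100 - 40.3 - 47.5 = 12.2% | consistent |
| 4B | 2/1/3 | 67.9% | 20.7% at the 0.383 dose; at most 32.1% | consistent |
| 5A | 0/0/6 | 0% | 13.8% | contradicted |
| 5B | 0/0/6 | 0% | 12.4% | contradicted |
| 6A | 3/1/2 | not stated | 100 - 51.6 = 48.4% unresolved | not checkable |
| 6B | 0/0/6 | 0% | about 56% | contradicted |
| 7A | 3/1/2 | not stated | 100 - 44.9 = 55.1% unresolved | not checkable |
| 7B | 0/3/3 | about 74% | at most 26% | consistent |

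**Step 3: the three contradicted rows.** The true rates are 0.341 to 0.599 (5A), 0.367 to 0.626 (5B) and 0.351 to 0.370 (6B). No dose lies below 0.33, so every declared MTD is an overdose and all other trials declared none:

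- 5A: 100 - 13.8 = 86.2% with no MTD.
- 5B: 100 - 12.4 = 87.6% with no MTD.
- 6B: 100 - 56 = about 44% with no MTD.

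The first two agree with the protocol's remark that most Scenario 5 trials stop early. In 6B the excess over the limit runs from 0.351 - 0.33 = 0.021 to 0.370 - 0.33 = 0.040.

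**Step 4: simulation error.** The standard error of 56% in 1000 trials is sqrt(0.56 x 0.44 / 1000) = 0.0157, about 1.6 percentage points. Chance does not explain the result.

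**Step 5: reading the sentence by whole scenario.** Averaging the two arms does not rescue it.

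- Scenario 5: overdose is (13.8 + 12.4)/2 = 13.1%, target 0%.
- Scenario 6: overdose is at least 56/2 = 28.0% (27.75% if the rounded figure was 55.5%). Target is at most (100 - 51.6)/2 = 24.2%, even if every Arm A trial without an underdose MTD chose the target dose.

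**Related description.** The Scenario 6 results paragraph assigns the flat overdose-range curve to BI 1387446. The scenario definition links the flatness to ezabenlimab data and the overdose level to BI 1387446. In Table 10.5: 2, however, the Scenario 6 Arm A row (BI 1387446 alone) equals Scenario 1 Arm A at all six doses, and the flat overdose-range row is Arm B. The reported results are labelled by arm and match the table.

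**The case against.** The strongest reply is that this is one over-broad phrase in an appendix. No reported percentage is wrong, the 56% is printed a few paragraphs above, and the assessment points the reader to Table 10.5: 3. The sentence feeds no rule: the overdose control and the MTD criteria stand in Section 7. Development of BI 1387446 has been terminated (SAP Section 4), so no escalation decision turns on it. All of this is fair and limits the weight of the point. It does not make the sentence true.

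Second, no design that ever declares an MTD could meet the comparison in Scenario 5, where no target dose exists, and the protocol explains why it finds those rates acceptable. This stands, and it makes Scenario 5 mainly a wording matter. It is a reason to exclude such rows from the claim.

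Third, the 6B rates are close to the limit. With 12 patients, the minimum per arm for declaring an MTD, the standard error of a 0.35 rate is sqrt(0.35 x 0.65 / 12) = about 0.14 even if all were treated at one dose, so a design can hardly separate 0.35 from 0.33. That softens the practical meaning of the 56%. But the sentence itself uses the 33% cut-off and fails on it.

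Fourth, the bounds for 1A, 6A and 7A are loose. The 42.2% in 1A counts as possible overdose every trial that chose one of the two lowest doses or declared no MTD. In 7A, with the same true curve, 44.9 - 31.4 = 13.5% chose those two doses. The bounds show only that these rows cannot be verified from the readable text and are not evidence of a further failure.

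**Conclusion.** The concern holds. The universal statement is wrong as written in 3 of 14 scenario-arms, which lie in 2 of the 7 scenarios. Scenario 6 Arm B is the only one of practical weight.

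The printed text supports the claim in eight scenario-arms and leaves 1A, 6A and 7A open, so three is a minimum count. The 0% target figures are not printed. They follow from Table 10.5: 2 on the assumption that a simulated trial can declare only one of the six tabulated doses as MTD. The defect is in how the operating characteristics are summarised. The model, the priors and the reported results are not in question.

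**What to change.** - Delete the opening words that extend the claim to every scenario, and add the exceptions. For example: *Where no planned dose lies in the target interval, a dose with true P(DLT) of at least 33% is declared MTD in about 56% (Scenario 6 Arm B), 13.8% (Scenario 5 Arm A) and 12.4% (Scenario 5 Arm B) of trials.*
- Limit the remaining claim to scenario-arms that contain a target dose and for which the sponsor confirms it against the full Table 10.5: 3, in particular 1A, 6A and 7A.
- Have the neighbouring statement about satisfactory results under misspecification refer to the 56%, and take any target-selection ranges from the full table.
- Reconcile the Scenario 6 description with Table 10.5: 2, for instance by saying that Arm A keeps the Scenario 1 curve and the flat overdose-range curve applies to Arm B.

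The cost is wording in one appendix and a check of three rows in a table the sponsor holds. The performance statement becomes less favourable. No re-run is needed, and no prior, threshold or escalation rule changes.

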11 DESCRIPTION OF GLOBAL AMENDMENT(S)

11.1 GLOBAL AMENDMENT 1

Date of amendment	25 Nov 2019
EudraCT number	2019-001082-32
EU number	
BI Trial number	1426-0001
BI Investigational Medicinal Product(s)	BI 1387446 BI 754091
Title of protocol	Phase I, first in human trial evaluating BI 1387446 alone and in combination with BI 754091 in solid tumours
Global Amendment due to urgent safety reasons	
Global Amendment	x
Section to be changed	Synopsis

Description of change	Revised description of established treatment options known to prolong survival to remove the word meaningfully.
Rationale for change	Revision in response to FDA review comment to remove the word “meaningfully” from this requirement as it is not clear/specific.
Section to be changed	Synopsis
Description of change	Revised description of Main Exclusion criteria
Rationale for change	Revision to align with Exclusion criteria #1 in Section 3.3.3
Section to be changed	Flowchart
Description of change	, at the 30-day safety follow-up, and at any time during the treatment period, if clinically indicated.
Rationale for change	Based on non-clinical data and the pharmacological activity of BI 1387446, it is considered that a potential risk of eye lens toxicity cannot be completely ruled out and therefore mitigation procedures must be in place in this FIH study.
Section to be changed	Flowchart
Description of change	Revised requirement for pregnancy test to be performed in serum in flowchart and footnote #5.
Rationale for change	Revision in response to MHRA review comment that pregnancy tests must be in serum.
Section to be changed	Flowchart
Description of change	Revised Footnote #10
Rationale for change	Revision added to clarify that a single ECG will be obtained as clinically indicated prior to drug administration, at least every two to three cycles.
Section to be changed	Flowchart
Description of change	Revised Footnote #13 to clarify that injection of BI 1387446 should be preferably performed immediately after completion of BI 754091 infusion.
Rationale for change	Revision added to align with Blood sampling flowcharts for Arms B and C.
Section to be changed	Flowchart
Description of change	Revision to footnote #27 to clarify safety parameters

Rationale for change	Revision added to clarify that prior to biopsy of deep visceral lesions appropriate safety lab parameters taken within 24h must be available.
Section to be changed	Flowchart
Description of change	Addition of Footnote #36 for lens opacity assessment.
Rationale for change	Based on non-clinical data and the pharmacological activity of BI 1387446, it is considered that a potential risk of eye lens toxicity cannot be completely ruled out and therefore mitigation procedures must be in place in this FIH study.
Section to be changed	
Description of change	Footnote #37 created and added to echocardiography
Rationale for change	Addition of footnote #37 to clarify that although echocardiography is the preferred method, MUGA scans are permitted to quantify LVEF. The same method should be used in a single patient throughout the trial.
Section to be changed	
Description of change	
Rationale for change	
Section to be changed	Flowchart
Description of change	Revised Footnote #23
Rationale for change	Revision added to clarify imaging should be performed via CT/MRI. PET-CT may be performed if clinically indicated based on tumour type, however, in this case a diagnostic-quality CT scan needs to be acquired as part of the PET-CT for RECIST measurements. The CT portion of a PET-CT can be used as the basis for RECIST measurements if the site has documented that a CT with appropriate radiation dose for diagnostic quality and IV/oral contrast was used (if not medically contraindicated).
Section to be changed	Blood Sample Flowchart: Arm A
Description of change	Description regarding triplicate ECGs at C1V1, moved from ECG to Event column. Description

	regarding triplicate ECGs at C2V1, and C5V1 updated and move from ECG to Event column.
Rationale for change	Revised column placement for clarity. For C2V1 and C5V1, revised to clarify that only 1 set of triplicate ECGs is required prior to sampling.
Section to be changed	Blood Sample Flowchart: Arm A, Blood Sample Flowchart: Arm B
Description of change	Revised to add footnote 6.
Rationale for change	Revision added to clarify that when triplicate ECGs are scheduled prior to blood sampling, the 3 single ECG recordings should be performed within a maximum period of 5 minutes prior to blood sampling.
Section to be changed	Blood Sample Flowchart: Arm B, Blood Sample Flowchart: Arm C
Description of change	Revised timing for BI 754091 administration
Rationale for change	Revision to clarify timing between BI 754091 and BI 1387446 administration on visits when both drugs are scheduled to be administered.
Section to be changed	Abbreviations
Description of change	Revised to align with check of abbreviations throughout document
Rationale for change	Revision to align with content updates for lens opacity assessment.
Section to be changed	Section 1.4.2
Description of change	Revised to add description of potential risk of eye lens toxicity. Clarification on classification of risks and terminology.
Rationale for change	Based on non-clinical data and the pharmacological activity of BI 1387446, it is considered that a potential risk of eye lens toxicity cannot be completely ruled out and therefore mitigation procedures must be in place in this FIH study.
Section to be changed	Section 3.1
Description of change	Revised to extend the DLT monitoring period to include echocardiographic/MUGA scan measurements acquired on Day 1 of Cycle 2 and related findings for MTD evaluability.
Rationale for change	Revision in response to FDA review comment.

Section to be changed	Section 3.1
Description of change	Revised to add statement that during dose escalation the BLRM will be evaluated after the occurrence of each DLT before enrolling any further patients at the respective dose level.
Rationale for change	Revision in response to MHRA review comment.
Section to be changed	Section 3.1
Description of change	Revised to remove statement “Further patients may be included to confirm this MTD estimate, i.e. to confirm that the EWOC criterion is still fulfilled.”
Rationale for change	
Section to be changed	Section 3.1.2
Description of change	Revised to clarify that following the occurrence of a drug related Grade 2 or greater AE, excluding asymptomatic Grade 2 laboratory abnormalities that resolve without medical intervention within 48 hours and transient Grade 2 local injection site reactions that resolve within 48 hours (whereby supportive treatment is allowed), a minimum of 3 patients will be required per dose cohort.
Rationale for change	Revised in response to FDA review comment.
Section to be changed	Section 3.1.3
Description of change	Revised description of locations where administration of BI 1387446 is not permitted.
Rationale for change	Revision in response to FDA review comment that injection into lesions which would be most often require the use of techniques other than percutaneous intratumoural injection, such endoscopic injection, is not permitted
Rationale for change	Section 3.3
Section to be changed	Revision to update wording regarding patient(s) determined eligible in error.
Description of change	Revision added to clarify that patients who may not meet eligibility are to be reported to the sponsor immediately. Patients are considered enrolled once informed consent has been signed and would be proceed to be assessed for eligibility.
Section to be changed	Section 3.3.2

Description of change	Revised Inclusion criteria #7 to remove word meaningfully.
Rationale for change	Revision in response to FDA review comment to remove the word “meaningfully” from this requirement as it is not clear/specific.
Section to be changed	Section 3.3.2
Description of change	Revised Inclusion criteria #11 to adjust concurrent creatinine clearance from ≥ 50 ml/min to ≥ 45 ml/min.
Rationale for change	Revision in response to FDA review comment.
Section to be changed	Section 3.3.3
Description of change	Revised Exclusion criteria #14 to exclude patients with any clinically important resting ECG abnormalities and factors that may increase the risk of QTc prolongation or risk of arrhythmic events.
Rationale for change	Revision in response to MHRA review comment. This change to exclusion criteria will ensure patient safety while allowing to enroll a population that more closely represents the intended future population.
Section to be changed	Section 3.3.3
Description of change	Added Exclusion criteria #22 for presence of any absolute contraindication to cataract surgery.
Rationale for change	Revision in response to MHRA review comment. Based on non-clinical data and the pharmacological activity of BI 1387446, it is considered that a potential risk of eye lens toxicity cannot be completely ruled out and therefore mitigation procedures must be in place in this FIH study.
Section to be changed	Section 3.3.3
Description of change	Added Exclusion criteria #23 for any factors that increase the risk of QTc prolongation or risk of arrhythmic events.
Rationale for change	Revision in response to MHRA review comment. This change to exclusion criteria will ensure patient safety while allowing to enroll a population that more closely represents the intended future population.
Section to be changed	Section 3.3.4.4

Description of change	Revised to clarify that patients withdrawn for a reason other than having a DLT, or who miss any dose of study medication during Cycle 1, are not evaluable for the MTD determination.
Rationale for change	Revision in response to MHRA review comment. Patients who miss more than one treatment visit during Cycle 1 are not evaluable for the MTD determination. Furthermore, none of the provisional dose levels for dose escalation (see CTP Table 4.1.2.1.1: 1) can be skipped during the dose escalation as the maximum allowable dose increment for the subsequent cohort will always be no more than 100% (see CTP Section 7).
Section to be changed	Section 4.1.2.1.2
Description of change	Revised to clarify the concentration of the ready to use solution will be [REDACTED] [REDACTED]
Rationale for change	Revision due to typographical error.
Section to be changed	Section 4.1.2.2
Description of change	Revised to remove statements "No dose escalation or de-escalation is foreseen. In case the recommended Phase II dose or schedule would be modified based on evidence from ongoing trials, the SMC may recommend to amend the dose of BI 754091 used in this study."
Rationale for change	Revision in response to FDA review comment.
Section to be changed	Section 4.1.4
Description of change	Revised to remove statements "BI 754091 is currently being used in several clinical trials. In case the recommended Phase II dose or schedule would be modified based on evidence from ongoing trials, the SMC may recommend to amend the dose of BI 754091 used in this study."
Rationale for change	Revision in response to FDA review comment.
Section to be changed	Section 4.1.4.4
Description of change	Revised to extend the DLT monitoring period to include echocardiographic/MUGA scan measurements acquired on Day 1 of Cycle 2 and related findings for MTD evaluability.
Rationale for change	Revision in response to FDA review comment.
Section to be changed	Section 4.1.4.5

Description of change	Revision to Table 4.1.4.5: 1 for clarification of collection of vital signs
Rationale for change	Revision to collection for superficial and non-visceral deep lesions.
Section to be changed	Section 4.1.4.6
Description of change	Revised to include minimum 8 hours of monitoring for CRS post-administration of Cycle 2 Day 1 dose of BI 1387446.
Rationale for change	Revision in response to FDA review comment.
Section to be changed	Section 4.2.2.1
Description of change	Revised to clarify that in Arms B and C, the use of live attenuated viruses has to be delayed until 70 days after the last dose of BI 754091 or 30 days after the last dose of BI 1387446, whatever comes later.
Rationale for change	Revision in response to MHRA review comment. The use of live vaccines should be prohibited until the end of the relevant systemic exposure (5 half-lives after the last dose) of the IMP with the longest half-life.
Section to be changed	Section 5.2.3
Description of change	Revised requirement in Table 5.2.3: 1 for pregnancy test to be performed in serum.
Rationale for change	Revision in response to MHRA review comment that pregnancy tests must be in serum.
Section to be changed	Section 5.2.3
Description of change	Revised Footnote #2 in Table 5.2.3: 1 to clarify if Nt proBNP not available, it may be replaced with a decline in preference by mid-regional pro-ANP, total BNP or ANP.
Rationale for change	Revision due to typographical error.
Section to be changed	Section 5.2.3
Description of change	Revised entry for Coagulation in Table 5.2.3: 1 to add PT
Rationale for change	Revision included to align with Inclusion criteria #11 in Section 3.3.2
Section to be changed	Section 5.2.3
Description of change	Revised footnote #4
Rationale for change	Revision included to clarify reference to FACS and to align with Section 5.4.2 and Flowchart

Section to be changed	Section 5.2.4
Description of change	Revised to clarify that in Arm C, single ECGs will be taken as clinically indicated, at least every two to three cycles. In case emerging data from the ECGs in Arm A and/or B suggest any potential signal, additional ECG measurements will be introduced in Arm C.
Rationale for change	Revision in response to FDA review comment.
Section to be changed	Section 5.2.4
Description of change	Revision to clarify that all ECGs will be transmitted to the central vendor for analysis.
Rationale for change	Revision included to clarify that central reading of all ECGs needed in support assessment of ECGs in relation to PK.
Section to be changed	Section 5.2.4
Description of change	Revised to add clarification that when triplicate ECGs are scheduled prior to blood sampling, the 3 single ECG recordings should be performed within a maximum period of 5 minutes prior to sampling.
Rationale for change	Revision added to align with Blood Sample Flowchart: Arm A and Blood Sample Flowchart: Arm B
Section to be changed	Section 5.2.6
Description of change	, at the 30-day safety follow-up, and at any time during the treatment period, if clinically indicated.
Rationale for change	Based on non-clinical data and the pharmacological activity of BI 1387446, it is considered that a potential risk of eye lens toxicity cannot be completely ruled out and therefore mitigation procedures must be in place in this FIH study.
Section to be changed	Section 5.2.7.2.2
Description of change	Revised to clarify that SAEs may be submitted to BI by means other than Fax.
Rationale for change	Revision to add administrative update.
Section to be changed	Section 6.2.1

Description of change	Revised to clarify the patient's reason(s) for not being eligible for established treatment options will be documented in the patient record and in the eCRF.
Rationale for change	
Section to be changed	
Description of change	
Rationale for change	
Section to be changed	Section 7.5
Description of change	Revised to remove statement "Fewer or more patients might be needed based on the recommendation of the SMC."
Rationale for change	Revision in response to FDA review comment.
Section to be changed	Section 8.6
Description of change	Revised to clarify the definition of the LPLVPE as the date on which the last patient finalised the first cycle and underwent echocardiogram/MUGA scan on Day 1 of Cycle 2.
Rationale for change	Revision in response to FDA review comment.
Section to be changed	Section 9.1
Description of change	Update of references
Rationale for change	Revised to align with check of references throughout document
Section to be changed	Section 10.1.2
Description of change	Revised management for immune-related AEs
Rationale for change	Revision to align with current instructions for the management of irAEs under treatment with PD1-inhibitor.
Section to be changed	Section 10.2

Description of change	Revised text for management of trial drugs for treatment of CRS.
Rationale for change	Revision to align with Section 4.1.4.3.
Section to be changed	Section 10.5
Description of change	Revised to add description of scenarios 02-06 and to updated Table 10.5: 1 to add scenarios 01-06.
Rationale for change	Revision in response to FDA review comment to address the possibility of enrolling cohorts of 1 at doses [REDACTED] in particular investigating scenarios in which the first dose level enrolls one patient who experiences a DLT.
Section to be changed	Section 10.5
Description of change	Revised Table 10.5: 4 to reflect the Inclusion and Exclusion criteria changes described for Sections 3.3.2 and 3.3.3.
Rationale for change	Revision to align with updates to other sections.
Section to be changed	Miscellaneous
Description of change	Revisions to formatting, punctuation, and/or spelling. Revision to update description of dose tier(s) to dose level(s).
Rationale for change	Clarifications added as applicable to address minor formatting updates and/or alignment of terms throughout document that do not affect protocol content and will not be listed as separate changes.

11.2 GLOBAL AMENDMENT 2

Date of amendment	26 May 2021
EudraCT number	2019-001082-32
EU number	
BI Trial number	1426-0001
BI Investigational Medicinal Product(s)	BI 1387446 Ezabenlimab (BI 754091)
Title of protocol	Phase I, first in human trial evaluating BI 1387446 alone and in combination with ezabenlimab (BI 754091) in solid tumours
Global Amendment due to urgent safety reasons	
Global Amendment	x

Section to be changed	Miscellaneous
Description of change	Revisions to denote that the start of Arm C will be postponed.
Rationale for change	The start of Arm C will be postponed until further evidence supporting a development in deep visceral tumours becomes available from Arms A and B.
Section to be changed	Miscellaneous
Description of change	Change BI 754091 to ezabenlimab (BI 754091)
Rationale for change	Compound name has been assigned. Updates have been added throughout the protocol in relevant sections.
Section to be changed	Synopsis, Section 2.1.3
Description of change	Revision to secondary endpoints
Rationale for change	Objective response will be based on Response Criteria for Intratumoural Immunotherapy in Solid Tumours (itRECIST). The best percentage change from baseline will be analysed in size of injected target lesions and in size of non-injected target lesions.
Section to be changed	Blood Sample Flowchart: Arm A
Description of change	Removal of blank timepoint at C5V1 12:00.
Rationale for change	Typographical error.
Section to be changed	Blood Sample Flowchart: Arm B
Description of change	Addition of triplicate ECGs at C1V1 at -1:15 and -1:35 and at C2V1 -1:05.
Rationale for change	Typographical error.
Section to be changed	Flowchart
Description of change	Addition of new footnote #4
Rationale for change	Clarification added that at Cycle 2 Day 1, an overnight stay is recommended if logistically possible due to sampling planned at the visit. Footnotes renumbered from this point forward.
Section to be changed	Flowchart
Description of change	Revision to footnote #34
Rationale for change	Clarification of the collection of echocardiography at Cycle 4 (within -7 days) and at Cycle 2 Day 1 (within 72 hours). Footnote is renumbered as #35 due to addition of footnote #4 described above.
Section to be changed	Section 1.4.2
Description of change	Revision to general safety measures for the trial.
Rationale for change	Addition of description of sequential start of backfill enrolment.
Section to be changed	Section 1.4.2

Description of change	Addition of language regarding potential identification of a confirmed SARS-CoV-2 infection.
Rationale for change	Adjustment added based upon an assessment of the COVID-19 related risks to trial participants.
Section to be changed	
Description of change	
Rationale for change	
Section to be changed	Section 3.1
Description of change	Clarification added regarding the start of the study arms and backfill enrollment.
Rationale for change	Arm A and B will start in a staggered manner (refer to Section 3.1.1). The start of Arm C will be postponed until further evidence supporting a development in deep visceral tumours becomes available from Arms A and B. To acquire additional data to more fully inform dose selection, additional patients may be enrolled to backfill cohorts at dose levels that have been previously cleared (refer to Section 3.1.1).
Section to be changed	Section 3.1.1, Figure 3.1.1:1
Description of change	Revisions to describe postponement of Arm C and clarification of handling of cross-over patients for MTD analysis.
Rationale for change	Figure 3.1.1: 1 revised to reflect postponement to start of Arm C. For the main analysis of the MTD, cross-over patients will only be included while being treated with BI 1387446 monotherapy in Arm A. However, cross-over patients will be included in the sensitivity analyses of the MTD and thus be considered in addition.
Section to be changed	Section 3.1.2
Description of change	Clarification added regarding the starting dose in Arm C and handling of DLTs in backfill patients.
Rationale for change	The starting dose in Arm C will depend on the highest dose determined to be safe for patients in Arm B. The starting dose may be delayed to a higher dose level to avoid putting patients at procedural risks for doses with lack of activity.

	
However, the starting dose in Arm C will fulfill the EWOC criterion and will be lower than the MTD and recommended dose, respectively, established for the combination of BI 1387446 and ezabenlimab (BI 754091) in superficial tumours. Furthermore, dose escalation in Arm C will start at least one dose level lower than the recommended starting dose based on the joint BLRM.
 
Backfill patients who have either experienced a DLT or have been observed for at least the MTD evaluation period without experiencing a DLT will be included into the main BLRM at the next subsequent SMC meeting. Particularly, in case DLTs are observed in 'backfill' patients, this information may affect the magnitude of dose escalation or even result in dose de-escalation. In case of the occurrence of DLTs, the SMC may decide about intervals between enrollment of patients, if applicable.

Section to be changed	Section 3.2
Description of change	Addition of language for the postponement to start of Arm C.
Rationale for change	The start of Arm C will be postponed.
Section to be changed	Section 3.3.2, Section 4.1.4.5, Section 10.5.4
Description of change	Addition of commonly used SI units.
Rationale for change	To provide clarification for laboratory parameters which are used for eligibility assessment and management of AEs.
Section to be changed	Section 3.3.4.1
Description of change	Revision to the criteria for discontinuation of trial treatment to address if a patient experiences an infection with SARS-CoV-2.
Rationale for change	Adjustment added based upon an assessment of the potential COVID-19 impact to trial participants.
Section to be changed	Section 3.3.4.4
Description of change	Clarification regarding replacement of patients
Rationale for change	A patient who misses the echocardiography/MUGA scan measurements acquired on Day 1 of Cycle 2 may be replaced.
Section to be changed	Section 4.1.2.3
Description of change	Clarification of treatment beyond progression
Rationale for change	PD assessment will be based on itRECIST and refers to the overall response assessment

	including all injected and non-injected lesions. Overall PD assessment after initial progression is comparable to iUPD with iRECIST (the possibility of iTPD will not be considered in this study).
Section to be changed	Section 4.1.3
Description of change	Clarification regarding the method of assigning patients to treatment groups.
